8.0 EFFICACY, VIROLOGY AND IMMUNE MEASURES

8.1 Clinical Efficacy

1. Transfer to ICU
2. 28 and 60 day mortality
3. Supplemental oxygen free days
4. Ventilator free days
5. ICU free days
6. Sequential organ failure assessment (SOFA) score at days 0, 1, 4, 7, 14, 21, 28
7. Need for vasopressors
8. Need for renal replacement therapy
9. Need for extracorporeal membrane oxygenation (ECMO)
10. Hospital length of stay (LOS)
11. ICU LOS
12. Grade 3 or 4 adverse events (AEs)

8.2 Virologic measures

1. Rates, levels and duration of SARS-CoV-2 RNA in OP or NP swabs and/or subgenomic - messengerRNA (sg-mRNA) from Viral Transport Media (VTM) by RT-PCR at days 0, 4, 7, 14, and 21. Other specimen types may be tested as available (e.g. BAL fluid, tracheal secretions, sputum, etc.) or when RT-PCR assays are validated for additional sources (i.e., stool, blood). VTM will be obtained from the original OP or NP swab collection devices as detailed above. Trial patient samples will be compared to control non-transfused hospitalized patient samples stored in the clinical labs.
2. Serologic positivity and neutralization antibody titers for anti-SARS-CoV-2 at days designated time points at 0, 7, 14, and 28.

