5.2.7 Enrollment, Screen Failures, and Study Completion

Patients are considered enrolled from time consented to participate until designated as a screen failure or have either been discontinued from the study or completed it. A screen failure is a patient who signed informed consent, but then was determined to be ineligible or withdraws from the study. Subjects are considered to have completed the study when they are followed through day 60 or have had an adverse event or death occurred prior to day 60.

Day -1 to 0 Baseline:

- A. Subject informed consent (obtained before performing study related activities)
- B. Baseline Evaluation at screening.
 1. Demographics (Age, sex ethnicity, race)
 2. Medical history (timing of exposure to COVID-19 source patient, acute and chronic medical condition, medications, allergies.) Any medical condition arising after consent should be recorded as AE.
 3. COVID-19 symptom screen (fevers, cough, shortness of breath, diarrhea, anosmia), onset of symptoms, source of contagion
 4. Vital signs

5. COVID-19 testing (RT-PCR) from nasopharyngeal, throat, tracheal aspirate or bronchoalveolar lavage and stool (optional) samples
6. Blood typing, CBC with differential, comprehensive metabolic panel
7. Serological testing: anti-SARS CoV-2 titers
8. Immune testing samples
9. Urine or serum pregnancy test for females of childbearing potential. Results from laboratory tests obtained up to 7 days before enrollment may be used for the pregnancy test.
10. Determination of eligibility as per inclusion/exclusion criteria, age, consent, positive for COVID-19, respiratory symptoms within 72 hours of admission

DAY 0 Baseline and Infusion:

1. Study Plasma Administration: 1-2 units of plasma will be transfused over 1-2 days. Time at start and end of infusion will be recorded and vital signs will be measured immediately prior to infusion, 10-20 minutes after start of infusion, at completion of infusion and 30-60 minutes after the end of the infusion
2. COVID-19 symptom screen (fevers, cough, shortness of breath)
3. Assessment of clinical status (8-point ordinal scale)
4. New medical conditions, concomitant medication, AE evaluation
5. Physical examination
6. COVID-19 testing (RT-PCR) from nasopharyngeal, throat or stool (optional) samples
7. Blood typing, CBC with differential, comprehensive metabolic panel, C-reactive protein
8. Serological testing: anti-SARS CoV-2 titers

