9. Blood for Immune evaluations of cellular and humoral immunity (4 green tops, 30-40 milliliters).

Day 1-7 (or for duration of hospitalization)

1. Vital signs daily (including supplemental oxygen requirements)
2. COVID-19 symptom screen (fevers, cough, shortness of breath)
3. Assessment of clinical status (8-point ordinal scale)
4. New medical conditions, AE evaluation
5. Physical examination
6. CBC with differential, comprehensive metabolic panel, CRP daily

Days 0, 4 (\pm 1 day), 7 (\pm 2 day), 14 (\pm 3 days), 21 (\pm 3 days), and 28 (\pm 3 days):

1. SARS-CoV-2 PCR from oropharyngeal or nasopharyngeal swabs: Day 0, 4, 7, 14, 21 and at any time when there is clinical suspicion for COVID-19.
2. Serum or plasma antibody titer to SARS-CoV-2: Day 0, 7, 14, and 28
3. Blood for immune evaluations of cellular and humoral immunity before CIP infusion (day 0) and 7, 14, and 28 days after CIP infusion (4 green tops, 30-40 milliliters). Immune testing may be done at any time if the PI determines there is a need to evaluate acute immune responses (cytokines/chemokines levels).

Key issues to consider follow up by phone, alive, at home, in hospital (ICU or not), on supplemental O₂ or not, back to work, fully and partially

- COVID-19 symptom screen (fevers, cough, shortness of breath)
- Assessment of clinical status (8-point ordinal scale)
- New medical conditions, AE evaluation

Day 60 (\pm 7 days):

1. COVID-19 symptom screen (fevers, cough, shortness of breath)

2. Assessment of clinical status (8-point ordinal scale)
3. New medical conditions, AE evaluation

One year (\pm 1 month) - *optional*

- 1. Serum or plasma antibody titer to SARS-CoV-2**
- 2. Blood for immune evaluations of cellular and humoral immunity**
- 3. CBC with differential, Comprehensive metabolic panel, PT/INR, PTT, Quantitative immunoglobulins**
- 4. Interval medical history**
- 5. Subject questionnaires regarding health status**

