SARS-CoV-2 RT-PCR (NP or OP)		x			x	x	x	x			
SARS-CoV-2 antibody		x				x	x		x		x
Blood for immune testing		x				x	x		x		x
PT/INR, PTT, Quantitative Immunoglobulins											x

ABO typing may be historical documentation of blood type ²Measured by an anti-SARS-CoV-2 ELISA and serum antibody titer to SARS-CoV-2. ³ Vital signs will be performed pre-transfusion, 10-20 mins after the start of transfusion, at completion and 30-60 mins after the end of the transfusion. ⁴Done daily through Day 7 or until patient is discharged from the hospital, whichever comes first ⁵Optional follow up visit for CIP recipients

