7.3.2 Secondary Endpoints

- Cumulative incidence of serious adverse events during the study period: transfusion reaction (fever, rash), transfusion related acute lung injury (TRALI), transfusion associated circulatory overload (TACO), transfusion related infection
- Rates and duration of SARS-CoV-2 PCR positivity at days 0, 4, 7, 14 and 21.
- Serum or plasma antibody titer³ to SARS-CoV-2: Day 0, 7, 14, and 28
- Cellular and humoral immune responses at days 0, 7, 14, and 28 days
- Supplemental oxygen free days
- Ventilator free days
- ICU free days
- Sequential organ failure assessment (SOFA) score at days 0, 1, 4, 7, 14, 21, 28
- WHO 8-point scale for clinical improvement at days 0, 1, 4, 7, 14, 21, 28
- Need for vasopressors
- Need for renal replacement therapy
- Need for extracorporeal membrane oxygenation (ECMO)
- Hospital length of stay (LOS)
- ICU LOS
- Grade 3 or 4 adverse events (AEs)

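### The PCR endpoint accepts an oropharyngeal (OP) or a nasopharyngeal (NP) swab at every visit, with no same-site rule within a patient and no site matching of stored controls, so a change of site can pass for a change in virus.

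*Combined protocol and SAP*

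**What the plan says.** The secondary endpoint in 7.3.2 is "Rates and duration of SARS-CoV-2 PCR positivity at days 0, 4, 7, 14 and 21" and names no specimen. Section 8.2 supplies one and adds RNA level: "Rates, levels and duration of SARS-CoV-2 RNA in OP or NP swabs". The follow-up schedule in 5.2.7 reads "SARS-CoV-2 PCR from oropharyngeal or nasopharyngeal swabs: Day 0, 4, 7, 14, 21", and the Table 1 row is labelled "SARS-CoV-2 RT-PCR (NP or OP" with no footnote about keeping to one site.

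Other specimens are mentioned in three places:
- The screening list in 5.2.7 is "COVID-19 testing (RT-PCR) from nasopharyngeal, throat, tracheal aspirate or bronchoalveolar lavage and stool (optional) samples".
- The day 0 list in 5.2.7 is narrower: nasopharyngeal, throat or optional stool.
- A separate sentence in 8.2 says "Other specimen types may be tested as available (e.g. BAL fluid, tracheal secretions, sputum, etc" and continues "or when RT-PCR assays are validated for additional sources (i.e., stool, blood".

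For the comparison, 8.2 sets trial samples against clinical-laboratory samples already held from hospitalised patients who were not transfused. It does not state the site of those samples. The only matching described in the plan is by gender and age, for the historic control group in 7.1. The analysis text in 9.1 does not mention swab site.

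**The concern.** Duration of positivity and RNA level are followed within a patient over time. They can be read as viral change only if the way of measuring stays the same. When the site may differ from visit to visit, a positive NP swab followed by a negative OP swab could mean that virus has gone or only that the second site detects less. The reverse switch could look like persistence or a return of virus. Levels are exposed in the same way unless the two sites yield comparable quantities, which the documents do not address.

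The between-group comparison has the same weakness. The stored samples were taken outside the trial, so their mix of sites is not under its control. The trial has a single arm, so no randomisation balances that mix. Section 3.2 cites reduced viral load among the reasons for studying plasma, so readers are likely to look to this endpoint for evidence of an antiviral effect.

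**Working it through.** **Step 1: the text.** The places that name a PCR specimen or a virologic analysis were set side by side: the Summary, 5.2.7, Table 1, 7.3.2, 8.2 and 9.1. Scheduled follow-up swabs are OP or NP wherever a site is given. No section requires the same site within a patient, names a preferred site, says how discordant sites are resolved, or stratifies by site. The plan gives no figure on this point, so there is nothing to reproduce.

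**Step 2: effect of switching within patients (illustration only).** Inputs:
- N = 29 treated patients (2.3).
- a = detection probability at the first site, assumed 0.90 or 0.95.
- b = detection probability at the second site, assumed 0.60 to 0.90.
- f = share of patients whose site changed, assumed 0.25 or 0.50, all in one direction.
- All 29 still truly positive at the visit.

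False-negative share with one site throughout = 1 − a.
False-negative share with switching = (1 − f)(1 − a) + f(1 − b).
The difference is f(a − b), so extra apparent clearances = 29 × f × (a − b).

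| a | b | f | One site | With switching | Extra of 29 |
|---|---|---|---|---|---|
| 0.90 | 0.90 | 0.50 | 10% | 10% | 0 |
| 0.90 | 0.80 | 0.25 | 10% | 12.5% | 0.7 |
| 0.90 | 0.70 | 0.50 | 10% | 20% | 2.9 |
| 0.90 | 0.60 | 0.50 | 10% | 25% | 4.4 |
| 0.95 | 0.90 | 0.25 | 5% | 6.3% | 0.4 |
| 0.95 | 0.60 | 0.50 | 5% | 22.5% | 5.1 |

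Over these assumptions the extra count runs from 0 to about 5.

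**Step 3: what shrinks or reverses it.**
- Equal detection (a = b) gives zero.
- If a share g switches the other way, the net effect is 29 × (f − g)(a − b), which is zero when f = g.
- If the second site is the more sensitive one (b > a), the sign reverses and the result looks like persistence.
- If only a share p is still positive, the count is multiplied by p. With p = 0.5, the 2.9 in the table becomes 29 × 0.5 × 0.5 × 0.20 = 1.45.

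**Step 4: effect between groups.** If trial and control samples differ in their share of the more sensitive site by d, positivity among truly positive patients differs by d × (a − b) with no true difference. With d = 0.50, a = 0.90 and b = 0.70, that is 0.50 × 0.20 = 10 percentage points. These values are also assumptions.

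**The case against.** The strongest reply is that nothing in the documents shows that the sites detect differently or that staff will switch between them. The illustration takes all switches in one direction and all patients as still positive, so it leans towards a large effect. The measure is one of many secondary endpoints. Section 9.1 specifies no test for PCR results and describes its analyses as exploratory, and comparison with non-randomised stored samples could not support a confirmatory antiviral claim anyway. All of this stands, and it limits the size and weight of the point. It does not remove the point, because the plan permits either site at each visit and offers no means of separating site from virus afterwards.

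Two stronger readings are tempting, and the documents do not support either.

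- **Pooling of other specimens.** A reader might infer that lower-respiratory or stool results are pooled into the endpoint, so that specimen type would depend on who was intubated. Section 8.2 ties rates, levels and duration to OP or NP swabs. Its sentence on other specimens is separate and does not say that they count. In 5.2.7, tracheal aspirate and lavage appear only in the screening list and not on day 0. Table 1 keeps a separate row for the eligibility PCR, and patients on mechanical ventilation are excluded at entry (4.2).
- **One negative swab ends the positive period.** A reader might infer this too, but no section defines clearance or how duration is counted. A fixed site would also still give some false negatives, as the 5% to 10% assumed above shows.

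**Conclusion.** The point holds for OP and NP swabs. As written, the plan can confound viral change within a patient, or a difference from stored controls, with the site sampled. This depends on unequal detection between the two sites, which is an assumption. The direction is not known in advance and the size cannot be computed from the documents. Zero is possible, and the figure of up to about 5 of 29 is a result of one-way assumptions, not an estimate for this trial. The primary endpoints, the sample size and the decision rule are not affected. The change is still worth making, because the remedy is cheap and a site not recorded at collection may not be recoverable later. The wording on subgenomic RNA in 8.2 and the missing definition of clearance are separate matters.

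**What to change.** In 5.2.7, Table 1 and 8.2:

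1. Use the same upper-airway site for each patient from day 0 to day 21 where feasible, and record the site of every swab on the CRF.
2. Compute levels and duration from scheduled swabs of that site.
3. Match or stratify the comparison with stored controls by site where their site is known.
4. Report off-site, lower-respiratory, stool and symptom-triggered samples separately, and state that they do not enter the endpoint.

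The cost is protocol and SAP wording plus one CRF field, with no additional swabs. The downside is some loss of data. Off-site trial samples leave the main virologic comparison, as do stored controls whose site is unknown or different. For the trial samples, the loss depends on how well the rule is followed. If switching stayed at the assumed 25% to 50%, it would touch about 7 to 15 of 29 patients (0.25 × 29 = 7.25; 0.50 × 29 = 14.5), so staff need the instruction before collection. The site of stored controls can no longer be chosen, so that set may shrink.

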2. Age \geq 18 years of age
3. No receipt of convalescent plasma

Immunologic Controls:

1. PBMCs with 5-10 million cryopreserved cells per specimen present in the prospective COVID 19 Biorepository
2. Serum or plasma 500 UI each from up to 50 patients present in the COVID-19 Biorepository

Assessment and Data Acquisition:

1. Baseline: Age, sex, comorbidities, date of symptom onset, known COVID-19 contact, type of admission to the floor or ICU, APACHE score (ICU scoring system to classify disease severity and mortality risk), SOFA score (mortality prediction score based on organ function), clinical status, vital signs including temperature, respiratory rate, oxygen saturation, oxygen requirement, neutrophil count, lymphocyte count, CRP, chest x-ray, chest CT, location in hospital.
2. Safety and efficacy: Day 0 (baseline), 1, 2, 3, 4, 7, 14, 21, and 28 and once at day 60.
3. SARS-CoV-2 PCR from OP or NP swabs: Day 0, 4, 7, 14 and at any time when there is clinical suspicion for COVID-19.
4. Outcome measures: increased O₂ requirement (PaO₂/FiO₂ ratio or SpO₂/FIo₂), supplemental oxygen strategy (nasal cannula, high flow nasal cannula, noninvasive ventilation, intubation and invasive mechanical ventilation, rescue ventilation i.e. neuromuscular blocking agents, prone positioning, corticosteroids, ECMO), vasopressors, renal support, ICU LOS, ICU mortality, hospital LOS, hospital mortality, 28 day mortality.
5. Serum or plasma antibody titer² to SARS-CoV-2: Day 0, 7, 14, and 28. Samples from the COVID-19 Biorepository from non-transfused patients will be assayed at two similar timepoints as Immunologic Controls.
6. Blood for immune evaluations of cellular and humoral immunity before CIP infusion (day 0) and 7, 14 and 28 days after CIP infusion. Immune testing may be done at any time if the PI determines there is a need to evaluate acute immune responses (cytokines/chemokines levels). Samples from the Prospective COVID-19 Biorepository from non-transfused patients will be assayed at two similar timepoints as Immunologic Controls.
7. "Clinical controls" will have all relevant datapoints collected via chart review (i.e. biospecimens will not be collected prospectively)

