2.3 Study Design

This is a single arm phase II trial to assess preliminary efficacy and confirm safety of infusions of anti-SARS-CoV-2 convalescent plasma in hospitalized patients with acute respiratory symptoms **with or without** confirmed interstitial COVID-19 pneumonia by CXR or chest CT. A total of 29 eligible subjects will be enrolled to receive high titer anti-SARS-CoV-2 plasma. Participants will be compared to a historical control group via retrospective chart review.

In addition, the following Immunologic Controls will be used to meet secondary objectives described above:

1. PBMCs with 5-10 million cryopreserved cells per specimen will be obtained from the prospective COVID 19 Biorepository (2 timepoints per patient t (60 specimens total) and assessed for cellular and humoral immune responses.
2. Serum or plasma 500 UI each from up to 50 patients in the Covid-19 Biorepository will be collected (2 timepoints from each patient) (100 total specimens) will be evaluated for antibody and cytokine responses.

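### Section 8.2 sets recipients' scheduled swabs against stored swabs from controls with no swab schedule, so late PCR positivity is open to selection and control duration cannot be derived

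*Combined protocol and SAP*

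**What the plan says.** Section 7.3.2 lists as a secondary endpoint "Rates and duration of SARS-CoV-2 PCR positivity at days 0, 4, 7, 14 and 21". For recipients, Section 5.2.7 schedules "SARS-CoV-2 PCR from oropharyngeal or nasopharyngeal swabs: Day 0, 4, 7, 14, 21", with extra swabs on clinical suspicion. The RT-PCR row of Table 1 marks the same days and does not carry the footnote that ends some assessments at discharge.

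For the comparator, the first item of Section 8.2, which covers rates, levels and duration of viral RNA, ends: "Trial patient samples will be compared to control non-transfused hospitalized patient samples stored in the clinical labs". It gives no sampling days, number of patients, swabs per patient, reason for swabbing or definition of day 0. The same item allows other specimen types, such as BAL fluid, tracheal secretions, sputum and stool, when available.

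The other control sources do not fill the gap. The Summary says that clinical controls "will have all relevant datapoints collected via chart review (i.e. biospecimens will not be collected prospectively". The biorepository supplies blood products only: PBMCs, and "Serum or plasma 500 UI each from up to 50 patients in the Covid-19 Biorepository will be collected (2 timepoints from each patient". Section 9 gives no method for comparing PCR rate or duration with controls, and no rule for missing or censored swabs.

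**The concern.** The two groups are sampled by different mechanisms. A recipient is due a swab on day 14 or 21 whether or not discharged. A control has a stored sample at that time only if still in hospital or tested again for a clinical reason. At late days the control group is therefore a selected subset, while the recipient group is meant to include everyone.

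If patients still in hospital shed virus for longer, late control positivity is raised, and plasma could appear to speed clearance when it does nothing. If repeat swabs are taken mainly to document clearance, the selection works the other way. Duration has a separate problem: it needs serial swabs up to a first negative, and nothing in the plan provides these for controls. Day 0 is the infusion day for recipients and has no defined counterpart in controls. What is at stake is the viral-RNA contrast with untreated patients.

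**Working it through.** The plan states no figure for this comparison, so there is none to reproduce. Positivity rates, discharge shares and control swabbing habits are not in the documents; every value for them below is an assumption.

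**1. Selection by hospital stay, no plasma effect.** Let h be the share still in hospital on a given day, p_in the positivity of those in hospital and p_out that of those discharged. Recipients, all swabbed, show h·p_in + (1−h)·p_out. Controls, swabbed only in hospital, show p_in. So

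gap (control − recipient) = (1−h)(p_in − p_out).

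- Day 14 with h = 0.4, p_in = 0.60, p_out = 0.30: recipients 0.4×0.60 + 0.6×0.30 = 0.42; controls 0.60; gap 18 points.
- Discharged share 0.4 to 0.8 and positivity difference 10 to 30 points: 0.4×0.10 = 4 points to 0.8×0.30 = 24 points.
- p_in = p_out: gap 0.
- p_in/p_out = 0.4/0.6, h from 0.8 to 0.2: gap −4 to −16 points.

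**2. Chance of a false signal.** Take h = 0.4 and p_in/p_out = 0.7/0.3. Recipients show 0.4×0.7 + 0.6×0.3 = 0.46 and controls 0.70. Suppose 29 recipients and 12 controls (about 40% of 29; Section 7.1 has 29 matched controls but does not say that they supply the swabs). By exact enumeration, Fisher's test at two-sided 0.05 is significant 24% of the time, against 4% when both rates are 0.5.

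**3. Selection by reason for swabbing.** Let q_pos and q_neg be the chances that a positive and a negative inpatient are swabbed. Observed control positivity is p_in·q_pos / [p_in·q_pos + (1−p_in)·q_neg]. With p_in = 0.60:

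| q_pos | q_neg | Observed control rate | Gap from recipients' 42% |
|---|---|---|---|
| 0.5 | 0.5 | 60% | +18 points |
| 0.8 | 0.4 | 75% | +33 points |
| 0.4 | 0.8 | 0.24/0.56 = 43% | about +1 point |
| 0.3 | 0.9 | 0.18/0.54 = 33% | about −9 points |

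**4. Duration.** A simulation assumed Weibull clearance times (shape 2, scale 16 days) and, independently, gamma-distributed stays (shape 2, mean 8 days). It generously gave controls every scheduled swab up to discharge. Clearance was observed in 16% of controls, against 82% on the full schedule to day 21. The mean last-positive day was 4.4 in controls against 10.7 on the full schedule. A naive control duration would thus look shorter, even where the late control rate looks higher.

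**The case against.** The strongest objection is that no late contrast is actually specified. Section 7.3.2 lists the PCR endpoint without a comparator, Section 9 names no PCR test against controls, and the sentence in Section 8.2 follows one about swab transport medium. It could mean no more than assaying stored material alongside trial samples. That reading is possible. However, the sentence closes an item on rates and duration at days 0 to 21 and limits the comparison to no particular day, so the ambiguity is itself a reason to write the limits down.

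A reader might infer that the control rate is inflated as a matter of fact. The documents do not support this: they give no positivity data, discharge times or reasons for control swabs, and steps 1 and 3 show how the gap can vanish or reverse. Nor do they say that a control discharged early has only an admission swab.

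The recipient side may also have gaps. The Summary's assessment list reads "SARS-CoV-2 PCR from OP or NP swabs: Day 0, 4, 7, 14 and at any time", omitting day 21, and Section 5.2.7 has "Key issues to consider follow up by phone, alive, at home, in hospital (ICU or not" without saying how a discharged recipient is swabbed. Missing late recipient swabs could narrow or widen the gap.

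A reader might also take this as the trial's only controlled virologic evidence. Section 8.2 counts antibody titers among its virologic measures, and the biorepository supplies controls for antibody. The point concerns viral RNA only.

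Finally, comparing inpatients only would condition on remaining in hospital after infusion, and length of stay is itself an endpoint. That objection stands and shapes the fix.

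**Conclusion.** The point holds for asymmetric sampling and for duration. Late control results are selected by hospital stay and by reason for swabbing, and control duration on the recipients' day 0-21 grid cannot be derived from what the plan provides. Raised late control positivity is plausible but not established. The illustrative artefact is 18 points, with a range of 4 to 24 points if inpatients are more often positive and are swabbed without regard to viral status. It is near zero or negative under heavy clearance testing, and naive control duration could err in the opposite direction from the rate. All these sizes rest on assumed inputs.

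The consequence is limited to a secondary virologic comparison in a plan that describes its control-biomarker analyses as exploratory. ICU transfer, 28-day mortality and the sample size of 29 are not touched.

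**What to change.** Amend Section 8.2 as follows.

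- Report day-14 and day-21 positivity and duration of positivity in recipients only, without a control contrast. Use OP/NP swabs only and treat duration as interval-censored between last positive and first negative swab.
- Limit any control comparison to the admission or day-0 swab and to early windows in which both groups have upper-airway swabs from the same site, aligned by days since symptom onset (already a baseline item in the Summary).
- Label that comparison descriptive, and show for each window the number swabbed out of the number eligible in each group.
- For windows after infusion, show recipients both overall and while in hospital, so that the effect of conditioning on a post-infusion outcome is visible.
- Report BAL, tracheal, sputum and stool results separately.

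The cost is protocol wording, a filter on data already planned, and symptom-onset dates from the charts of whichever patients supply the stored swabs. No new samples are needed. The late-day and duration contrasts with controls are lost; as specified, the control samples cannot support the duration contrast and leave the late-day contrast open to selection.
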